NOTE: Follow-up assessments will be conducted after 6 months post-intervention. They will occur in November 2012 for the Spring group and in February 2013 for the Summer group.

INCLUSION/EXCLUSION CRITERIA

All individuals invited to participate in the study will be parents of children with developmental delays and clinically significant behavior problems. When there are two parents in the family, both parents will be invited to participate in the study; however, two parents from the same family will only count as one family. In other words, we plan to recruit the parent(s) of 90 children with developmental delays. Criteria for study entry are: (1) Having a child ages 3 to 5, (2) child has been determined by Regional Center (or by an independent assessment) to have a developmental delay, (3) parent(s) report more than 10 child behavior problems (the recommended cutoff score for screening children for treatment of conduct problems) on the Eyberg Child Behavior Inventory (ECBI; Robinson, Eyberg, & Ross, 1980), (4) the parent(s) is not receiving any form of psychological or behavioral treatment at the time of referral (e.g. counseling, parent training, parent support group, etc.), (5) parent(s) agree(s) to participate in the intervention (this requirement will be determined based on whether the parent(s) signs the consent form), and (6) parent(s) must speak and understand English.

Exclusion criteria include parents of children with debilitating physical disabilities or severe intellectual impairments that prevent them from participating in the assessment tasks described in the protocol (e.g. child is not ambulatory). As mentioned above, the child is only involved in the assessment aspects of the study pre-intervention, post-intervention, and at follow-up. During these assessments the child is instructed to play on the floor with the parent for 25 minutes. This task requires the child to understand the researcher's directions, sit-up on his/her own, explore different toys in the room, and interact with the parent. Therefore, if the child has a physical disability or severe intellectual impairment that prevents him or her from participating in the play task the family will be excluded from the study.

Robinson, E. A., Eyberg, S. M., & Ross, A. W. (1980). The standardization of an inventory of child conduct problem behaviors. *Journal of Clinical Child Psychology*, 9, 22-29.

SUBJECT RECRUITMENT & SCREENING

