The goal is to recruit 90 families during the first 5 months of the study (October through February). When there are two parents in the family, both parents will be invited to participate in the study; however, two parents from the same family will count as one family. In other words, we plan to recruit the parent(s) of 90 children with developmental delays. We anticipate that about 20% of the sample will not complete the intervention leaving a total sample of about 70 families for the complete study. According to power calculations, sample size of 70 is sufficient to detect a medium size effect with a power of .80, giving us an 80% chance of detecting a significant effect if it is there.

Participants will be limited to parents of children ages 3 to 5 who are English-speaking. The rationale for the age restriction is that parents of children often exhibit heightened stress during the preschool years, while simultaneously experiencing a reduction in services because Early Start services in California terminate when the child is 3 years of age ([name], Green, & Baker, in press).

This intervention is targeted for this specific risk group. Additionally, all parents must speak and understand English because the Principal Investigator who will be delivering the intervention is monolingual English speaking. Other than these two restrictions, recruitment will be open to parents of all races/ethnicities, socio-economic classes, sexual orientations, and religions.

In terms of vulnerable subjects, this research primarily involves parents of children with developmental delays and elevated behavior problems. The research focuses on the questions of (1) how parental stress contributes to subsequent behavior problems in children with delays and (2) how reducing parental stress and promoting parent's mental health impacts children's behavior over time. Children will only be asked to participate in a 25-minute play assessment pre and post-intervention as well as at the follow-up assessment. This study is minimal risk to children and their families.

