- Hypothesis: Parenting behavior will mediate the relationship between parenting stress and child behavior problems such that, once parenting behavior is accounted for, the relationship between parenting stress and child behavior problems will be significantly reduced (partially mediated) or no longer significant (fully mediated).

Aim 6: To examine variables that may moderate the effect of the intervention (reducing parental stress) on child behavior problems.

- Hypothesis: The effect of the intervention in reducing parents' levels of stress and children's subsequent behavior problems will be greater for parents with less social support (e.g. marital adjustment, family support) and who have fewer psychological resources (e.g. low dispositional optimism, less feelings of self-mastery), are less satisfied with their parenting, and have a more negative relationship with their child pre-intervention. Additionally, parents of children with more difficult temperaments will also evidence greater intervention gains.

References

Wierzbicki, M., & Pekarik, G. (1993). A meta-analysis of psychotherapy dropout. *Professional Psychology: Research and Practice*, 24(2), 190-195

Procedures

Interested parents will either contact the MAPS project by phone, return a postcard requesting the PI to contact them, or submit their information on the MAPS website. If the family indicates interest in participation, the PI will conduct a phone screen (please refer to enclosed phone screen document). If the family meets eligibility for the study, an appointment will be scheduled for the initial laboratory assessment.

Prior to the initial laboratory assessment, parents will be mailed a packet of questionnaires that they will complete prior to coming into the lab. Only parents participating in the study will complete the packet; however, each parent's significant other (or if it is a single parent family another significant adult in the child's life) will complete two questionnaires (one about the child's behavior problems and about the child's social skills) in order to minimize shared method variance.

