At the initial assessment, parents will be given an informed consent form that the PI or her staff will review with the parent (see informed consent procedures described above). After that, the parent and the child will participate in a 25-minute play assessment in the lab, which will be videotaped for later coding. Parent and child will be given a standardized set of toys and there

are 3 parts of the assessment: (1) *Child-led play* (parent is instructed to allow the child to choose any activity and play along with the child); (2) *Parent-led play* (parent is instructed to select an activity and to keep the child playing according to the parent's rules); and (3) *Clean-up* (parent is instructed to give the child a command to clean up). This task is standard procedure for the Dyadic Parent-Child Interaction Coding System (DPICS, Robinson & Eyberg, 1981), which will be used in this study to measure parenting behavior. After the observation task with the child, parents will meet with the experimenter to complete a demographic questionnaire and the Children's Global Assessment of Functioning Questionnaire. Parents will also be given a letter and two questionnaires for the child's teacher to complete. After completing these measures, the parents will draw a piece of paper out of a box which informs them whether they will be in the spring or summer intervention group.

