Dyadic Parent-Child Interaction Coding System (DPICS)	X	X	X	Coding system that measures parenting behavior including the following codes: Positive Parenting (DPICS-PP; includes praise, positive affect, and physical positive); Negative Parenting (DPICS-NP; includes negative commands, critical statements, and physical negative); and Total Commands (DPICS-TC; includes indirect and direct commands).	Lab Observation
Alabama Parenting Questionnaire-Parent Global Report	X	X	X	This questionnaire will be used to assess self-reported parenting practices. The APQ consists of 42 items presented with a 5-point endorsement scale (Never, Almost Never, Sometimes, Often, Always), which map onto five subscales (Poor Monitoring and Supervision, Inconsistent Discipline, Corporal Punishment, Positive Parenting Techniques, Parental Involvement), as well as the three broad factors structure (Positive Involvement, Negative/Ineffective Discipline, Deficient Monitoring). The APQ is a widely used self-report measure of parenting behavior.	Parent-Report
Parent Practices Interview	X	X	X	This questionnaire was adapted from the Oregon Social Learning Center's (OSLC) discipline questionnaire and revised for young children. The PPI can be administered as an interview or used as a self-report questionnaire completed by the child's primary caregiver. It has the following composites: Harsh Discipline, Harsh for Age, Inconsistent Discipline, Appropriate Discipline, Positive Parenting, Clear Expectations, and Monitoring.	Parent-Report

Measure	Pre-Tx	Post-Tx	Follow-Up	Description	Type of Measure
CCNES: Coping with Children's Negative Emotions Scale	X	X	X	A 72-item questionnaire measuring the degree to which parents perceive themselves as reactive to young children's negative affect in distressful situations. Six subscales are derived that reflect the specific types of coping responses parents tend to use in these situations (distress reactions, punitive reactions, expressive encouragement, emotion-focused reactions, problem-focused reactions, and minimization reactions).	Parent-Report
Measures of Moderating Variables					
Dyadic Adjustment Scale (DAS)	X	X	X	32-item self-report measure of marital adjustment. It has 4 subscales: Dyadic Consensus, Dyadic Satisfaction, Affectional Expression, and Dyadic Cohesion	Parent-Report

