Data analysis will primarily use parametric statistics to examine (1) whether there is a significant reduction in parenting stress as a result of the intervention (e.g. dependent sample t-tests), (2) whether there is a significant reduction in children behavior problems as a result of the intervention (e.g. dependent sample t-tests), (3) whether parenting behavior mediates the relationship between reductions in parenting stress and subsequent reductions in child behavior problems (e.g. hierarchical multiple regression and univariate analysis of variance), and (4) whether the impact of the intervention on parenting stress and/or children behavior problems changes as a function of the specified modifying variables (e.g. hierarchical multiple regression and univariate analysis of variance). Hierarchical Linear Modeling (HLM) may be employed after the project is completed to examine growth trajectories of the variables of interest over time.

POTENTIAL RISKS AND DISCOMFORTS

Risks for participants are minimal. All procedures for this study have been used widely in previous research, with little to no discomfort or risk to either the parents or the child. Nevertheless, some of the questions in the questionnaires and interviews do seek personal information, and might be considered an invasion of privacy (e.g. questions about the marriage). Only the parent is asked to provide information and complete questionnaires. The child is not interviewed or asked to complete any measures. However, the child is asked to participate in a play task with the parent(s) and during this task the child might experience some mild frustration (e.g. during the clean-up task). In the PI's experience using these tasks in similar studies, the risks or likelihood of discomfort is minimal. Additionally, if the parent and/or child decide to not complete the assessment (e.g. not complete a questionnaire, refuse to participate in the play assessment) the family will still be compensated for the assessment. The parent(s) and child have the right to refuse to answer any question or terminate their involvement in the study at any time.

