Institutional Review Board
Approved *[name]*
Date *12/14/17*

RECEIVED

JUL 03 2018

LLUH Responsible
Research Services

Institutional Review Board CHANGE REQUEST FORM

RESEARCH PROTECTION PROGRAMS | LOMA LINDA UNIVERSITY | Office of Research Affairs
[name] [contact] (voice) / [contact] (fax)/e-mail: [contact]

Principal Investigator: [name]

Department: Psychology

Protocol Title: Mindful awareness for parenting stress (MAPS) project for parents of children with developmental delays

IRB #: 5110264

Approval End Date: Aug 20, 2018

Current Stipulations: N/A

I. This Change Request is a result of: (check all that apply)

- Initiated by Sponsor.
- Initiated by local (LLU) Investigator.
- Result of Adverse Event;
re: AE report submitted: ("Unique Identifier")
- Protocol change was necessary to eliminate apparent immediate hazards to subject(s).

II. Protocol Change(s):

- a. Briefly summarize this Change Report, using the preferred wording to appear in the IRB's approval letter.
(This is also the only description appearing in future protocol profiles.)

We are submitting changes to our phone screen, consent form, and questionnaire measures to be consistent with our recently awarded NIH grant (LLeRA 2170159) which falls under this IRB. More specifically, for the phone screen, we are going to ask parents whether their child has an autism spectrum diagnosis, administer the Parenting Stress Index-Short Form 4th Edition instead of the Perceived Stress Scale during the phone screen, and screen for exclusionary criteria. A very similar phone screen was approved for another study of mine (HS 5170325) and these questions have worked very well.

With regard to the consent form changes, we have updated the our previous consent form from the MAPS project to reflect the revised aims and procedures for the NIH grant. We have included a clean copy of our new consent form (title is Stress-reduction techniques for effective parenting skills (STEPS) project), our previous MAPS consent with the track changes, as well as a clean copy of the approved MAPS consent form in order to make the changes clear.

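### Aim 5 calls mediation full when the adjusted stress coefficient is not significant; with about 70 families a real direct effect will often pass as none

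*Combined protocol and SAP*

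**What the plan says.** The criterion stands in the hypothesis under Aim 5 in Objectives. After adjustment for parenting behaviour, the stress and child-behaviour relationship "will be significantly reduced (partially mediated) or no longer significant (fully mediated". The two outcomes are alternatives. As worded, the full branch does not itself ask for a significant reduction, and the words *no longer* imply that the unadjusted association was significant first.

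Data Analysis describes the third analysis as whether parenting behaviour "mediates the relationship between reductions in parenting stress and subsequent reductions in child behavior problems (e.g. hierarchical multiple regression", with univariate analysis of variance as a second example. It names no test or interval for the indirect effect and no bound on the direct effect.

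Subject Recruitment & Screening sets the size: "The goal is to recruit 90 families during the first 5 months of the study", with about 20% expected not to finish, "leaving a total sample of about 70 families for the complete study". It claims power of .80 for a medium effect without naming the test.

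Inclusion/Exclusion Criteria allows both parents to take part, although "two parents from the same family will only count as one family". The later Change Request Form says the consent form was updated "to reflect the revised aims and procedures for the NIH grant"; those revised aims are not in the visible text.

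**The concern.** Failing to reject a zero coefficient does not show that it is zero. When the test has little power, a non-significant result is the expected outcome for a modest real effect. The full branch therefore gives its strongest mechanistic conclusion where the data are least able to support it. Readers could be told that parenting behaviour explains the whole link between parental stress and child behaviour when a direct link remains.

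The implied first step works in the opposite direction. If the total association must be significant before anything can be called mediated, complete mediation through two moderate paths produces a small total effect and often cannot qualify.

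Aim 5 is the study's mechanism claim. Aims 1 to 4 and 6 do not depend on this rule.

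**Working it through.** **The plan's own figures.** 90 × 0.80 = 72, which the plan rounds to about 70. The .80 power depends on the unnamed test. At N=70 and alpha 0.05, a regression F test with f² = 0.15 and two predictors gives 0.82. A two-sided test of a correlation of 0.30 gives 0.72. Two groups of 35 with d = 0.5 give 0.55. So the figure can be reproduced, but it says nothing about power for the direct effect in Aim 5.

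**Assumed inputs.** N=70 is the only analysed size in the visible text. Two-sided alpha 0.05 and the path sizes are assumptions. Stress (X), parenting behaviour (M) and child behaviour (Y) are standardised, with a the X→M path, b the M→Y path and c′ the direct effect.

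**Formulas.**
- Total effect = ab + c′.
- Residual variance of Y: v = 1 − (c′² + b² + 2abc′).
- SE(c′) ≈ √[v / (67(1 − a²))], where 67 = 70 − 3.

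**One cell by hand** (a=b=0.39, c′=0.14):
- v = 1 − (0.0196 + 0.1521 + 0.0426) = 0.7857.
- SE = √[0.7857 / (67 × 0.8479)] = 0.118, so c′/SE = 1.19.
- The noncentral t distribution gives power of about 0.22, so the coefficient is non-significant in about 78% of trials.

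**Precision at zero.** With a=b and c′=0, v = 1 − a², so SE = √(1/67) = 0.122. The 95% half-width is 1.996 × 0.122 = 0.24. Even an estimate of exactly zero leaves direct effects up to about 0.24 in either direction compatible with the data.

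**Simulation** of X→M→Y with OLS t tests at N=70. There were 40,000 trials per cell or more, and 600,000 in the a=b=0.26 rows. Entries are percentages.

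| a=b | c′ | c′ non-significant | total significant | both (full label) | label, given total significant |
|---|---|---|---|---|---|
| 0.26 | 0 | 95 | 9 | 6 | 65 |
| 0.26 | 0.14 | 79 | 41 | 20 | 49 |
| 0.26 | 0.20 | 61 | 62 | 23 | 37 |
| 0.39 | 0 | 95 | 24 | 22 | 89 |
| 0.39 | 0.14 | 78 | 70 | 48 | 69 |
| 0.39 | 0.20 | 59 | 86 | 45 | 52 |
| 0.50 | 0 | 95 | 56 | 53.5 | 96 |
| 0.50 | 0.14 | 77 | 92 | 70 | 75 |
| 0.50 | 0.20 | 56 | 98 | 54 | 55 |
| 0.60 | 0 | 95 | 87 | 84 | 96 |
| 0.60 | 0.14 | 76 | 99 | 75 | 75 |
| 0.60 | 0.20 | 51 | 100 | 51 | 51 |

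The last column is the fifth divided by the fourth before rounding. In the first row this is 5.57 / 8.63 = 64.5%. At a=b=0.55 and c′=0.14 it reaches 76%, the highest value for a real direct effect.

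**Without the total-effect requirement.** Under complete mediation, requiring only that a and b are both significant finds mediation in about 32%, 81% and 97% of trials at a=b=0.26, 0.39 and 0.50. A percentile bootstrap interval for ab finds it in 31%, 81% and 97%.

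**The case against.** The best defence is that the sentence is a hypothesis, not an analysis rule. Its main clause says that parenting behaviour will mediate, and full and partial only describe how. In OLS the fall in the stress coefficient equals ab, so the *significantly reduced* branch already points to an indirect-effect test, and only its name is missing. This is fair for the partial branch. It does not rescue the full branch, and Data Analysis supplies no other criterion.

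A reader might infer that a real direct effect of 0.14 to 0.20 earns the full label at least as often as no direct effect, so that the label carries no information. The documents do not support that. It is true per trial only for some assumed paths, up to about a=b=0.50. There it arises because adding a direct effect with a and b fixed also raises the total effect: at 0.39, from 0.15 to 0.29 or 0.35, which lifts the power of the total-effect test from 24% to 70% or 86%. At a=b=0.60 the order reverses (84% for complete mediation against 75% and 51%). It also reverses when only the adjusted coefficient is tested, when the rate is taken among trials with a significant total effect, and when the total is held at 0.30 (70% against about 50% to 53% for 0.14 and 32% to 40% for 0.20).

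Nor should one infer that the rule commonly finds full mediation where there is none. With b=0 and a direct effect of 0.30, the label appears in 7% to 15% of trials for a between 0.3 and 0.5 on the most literal reading, but in only about 1% if a and b must also be significant.

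Two limits stand. The simulation has no treatment arm, baseline adjustment or change scores, although Data Analysis speaks of reductions. And N=70 and Aim 5 belong to the 2011–12 waitlist design, while the 2018 change request concerns children with autism and its phone screen describes two active groups.

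**Conclusion.** The point holds in a limited form. The full branch of Aim 5 reads non-significance as absence. For a=b of 0.26 to 0.60, a direct effect of 0.14 to 0.20 would be missed in about half to four-fifths of trials. The label is more likely under complete than partial mediation once the total effect is significant, but the ranges across the assumed paths overlap (about 65% to 96% against 37% to 76%), so a full label cannot be taken to mean that no direct effect remains. The implied total-effect requirement is a second, separate loss: at a=b=0.39 it leaves complete mediation recognised as full in 22% of trials, although a and b are both significant in 81%.

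These sizes rest on assumed paths, alpha and normal data at N=70. That a non-significant coefficient does not establish a zero effect needs none of those assumptions. This should be changed, but it bears on Aim 5 only.

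**What to change.** Reword the Aim 5 hypothesis to predict a non-zero indirect effect. Drop the full and partial labels and the need for a significant total effect. In Data Analysis, state that mediation will be judged by ab with a 95% confidence interval, and that the direct effect will be reported with its own 95% interval and not be concluded to be zero.

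A percentile bootstrap is one suitable interval. A joint test of a and b has similar power, so the gain comes from removing the total-effect requirement and not from the bootstrap. Whatever method is used should treat the family as the unit, because two parents of one family may take part. In simulations with no mediation (a=0.5, direct effect 0.30, half to all families with two parents, assumed within-family correlation 0.5 to 0.7), the interval wrongly excluded zero in 8% to 12% of trials when parents were resampled and in 6% to 7% when families were.

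Writing that sentence will also require naming the mediator score and the assessment waves, which the plan leaves open.

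The cost is one reworded hypothesis, a sentence or two of analysis text and short code. No new data are needed. The Aim 5 conclusion becomes less categorical. Before editing, confirm that the revised aims mentioned in the Change Request Form still contain this criterion.

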Mindfulness and Parent Stress Reduction:
Improving Outcomes for Children With Autism
Spectrum Disorder

NCT03459625

16JUL2018

PROTOCOL

PROJECT INFORMATION

Project Title: Mindfulness Awareness for Parenting Stress (MAPS) Project for Parents of Children with Developmental Delays

Funding: Funding comes from [name] start-up research funds that she received as part of her package at Loma Linda University

Phase of Study: This is the first phase of MAPS study and the first IRB application that has been submitted for this study.

PRINCIPAL INVESTIGATOR'S INFORMATION

Principal Investigator: [name].

- Address: Loma Linda University, Department of Psychology, [name]
- [contact]
- Email: [contact]

STUDY PERSONNELL

All other personnel are currently doctoral students in the Ph.D. or Psy.D. Clinical Psychology programs at Loma Linda University. Their names are listed below and their certificates certifying that they have completed the human subjects training are also include in this application.

Name	Doctoral Program at LLU	Year in Program
[name]	Ph.D. in Clinical Psychology	2 nd
[name]	Psy.D. in Clinical Psychology	2 nd
[name]	Psy.D. in Clinical Psychology	2 nd
[name]	Ph.D. in Clinical Psychology	3 rd
[name]	Ph.D. in Clinical Psychology	1 st
[name]	Ph.D. in Clinical Psychology	1 st
[name]	Psy.D. in Clinical Psychology	2 nd

STUDY INFORMATION

The MAPS Project is a low-risk social/behavioral study that examines the efficacy of a stress-based intervention for parents of children with developmental delays (see description below for more detail). Laboratory assessments will take place in [name] laboratory in the Psychology Department ([name], Rooms 5 and 6). The intervention will be delivered at the Behavioral Health Institute ([name]).

Timeline for the study is as follows:

	Oct '11	Nov '11	Dec '11	Jan '12	Feb '12	Mar '12	April '12	May '12	June '12	July '12	Aug '12	Sept '12
Recruitment (N=90)	X	X	X	X	X							
Pre- Intervention Group Assessments for Spring and Summer Groups (N=90)		X	X	X	X							
Spring Group Intervention (N=45)						X	X					
Post- Intervention Assessments for Spring Group (N=45)								X				
Second Pre- Intervention Assessment for Summer Group (N=45)									X			
Summer Group Intervention (N=45)									X	X		
Post- Intervention Assessments for Summer Group (N=45)											X	

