Informed consent will be obtained at the first laboratory assessment. Parents will be given the informed consent form (see included consent form) and asked to read the form. If the parent prefers, the experimenter will read the form to the parent. The experimenter will also provide a summary of study (e.g. timeline for intervention, expectations with regard to pre, post and follow up assessments, compensation, components of assessment, and potential risks of study). Parents will be informed that intervention group assignment is random and that they may be assigned to the Spring group (March through April 2012) or the Summer group (June through July 2012). The experimenter will be available to answer any and all questions the parent(s) has and to address any concerns. Parents will be reminded that their consent is voluntary, that they can withdrawal from the study at any point, and that they do not have to answer any question or participate in any task that they do not want to. Given the young age of the children in the study (ages 3 to 5), parents will consent for their own and their child's participation. The PI for this project has had extensive training in conducting research with similar families and has completed the HIPAA compliance training online (certificate is included). Graduate students working on

the project as research assistants have also completed the HIPAA training online and are completing training with the PI on providing informed consent and administering the standardized protocol.

STUDY DESIGN

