Sanders, J. L., & Morgan, S. B. (1997). Family stress and adjustment as perceived by parents of children with autism or down syndrome: Implications for intervention. *Child & Family Behavior Therapy*, 19(4), 15-32.

Singh, N. N., Lancioni, G. E., Winton, A. S. W., Fisher, B. C., Wahler, R. G., McAleavey, K., . . . (2006). Mindful parenting decreases aggression, noncompliance, and self-injury in children with autism. *Journal of Emotional and Behavioral Disorders*, 14(3), 169-177.

Singh, N. N., Lancioni, G. E., Winton, A. S. W., Singh, J., Singh, A. N., Adkins, A. D., & Wahler, R. G. (2010). Training in mindful caregiving transfers to parent-child interactions. *Journal of Child and Family Studies*, 19(2), 167-174.

Yirmiya, N., & Shaked, M. (2005). Psychiatric disorders in parents of children with autism: A meta-analysis. *Journal of Child Psychology and Psychiatry*, 46(1), 69-83.

Objectives

Aim 1: To determine whether MBSR is a feasible intervention with parents of children with developmental delays.

- Hypothesis: The majority of parents (minimum of 60%) who enter the program complete the full 8 weeks of the program. Although we hope for less attrition, this is a conservative estimate given that attrition from child psychotherapy in general is high, ranging from 40% to 60% (Wierzbicki & Pekarik, 1993).

Aim 2: To examine whether MBSR leads to reductions in parenting stress.

- Hypothesis: Parents will self-report significantly lower levels of stress post-intervention and at follow-up.

Aim 3: To investigate whether MBSR is associated with changes in parenting behavior.

- Hypothesis: Parent receiving the intervention will exhibit less negative and intrusive behavior and more positive and sensitive behavior compared to controls as evidenced in observational as well as self-report measures.

Aim 4: To determine whether reductions in parenting stress are associated with decreases in child behavior problems at post-intervention and at follow up.

- Hypothesis: Children of parents receiving MBSR will show greater reductions in behavior problems compared to children of waitlisted parents as evidenced by the participating parent, spouse/significant other, and teacher reports.

Aim 5: To evaluate whether parenting behavior mediates the relationship between parenting stress and child behavior problems.

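### The tests named for both efficacy questions are within-person paired t-tests; no between-arm comparison is specified, so the randomised contrast in Aim 4 goes untested

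*Combined protocol and SAP*

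**What the plan says.** The Data Analysis section lists four analyses. The first is "whether there is a significant reduction in parenting stress as a result of the intervention (e.g. dependent sample t-tests". The second is "whether there is a significant reduction in children behavior problems as a result of the intervention (e.g. dependent sample t-tests". Both attribute the change to the intervention, and neither names a comparator. Hierarchical regression and univariate ANOVA appear only under mediation and moderation. Hierarchical linear modelling is optional, is described only for growth trajectories, and has no arm or arm-by-time term.

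The design is comparative. The Informed Consent Process section says "Parents will be informed that intervention group assignment is random", to the Spring or the Summer group. The Aim 4 hypothesis under Objectives is that "Children of parents receiving MBSR will show greater reductions in behavior problems compared to children of waitlisted parents". The Aim 3 hypothesis also refers to controls. The Aim 2 hypothesis names no comparator: "Parents will self-report significantly lower levels of stress post-intervention and at follow-up". The timeline under Study Information includes a "Second Pre- Intervention Assessment for Summer Group (N=45"), which is an untreated measurement of the waitlist arm.

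The 2018 phone-screen script describes random assignment to a mindfulness group or an educational parent support group. The text available contains no revised analysis section for that design.

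**The concern.** A paired test asks whether scores moved between two visits. It does not ask whether they moved more than they would have without MBSR. In the waitlist design it mixes the treatment effect with any change over time. In the support-group design it would also credit MBSR with whatever attending any group produces.

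The error can go either way. If scores drift down on their own, an ineffective programme can look effective. The Background section, however, says that stress in these parents may persist or grow, and in that case a paired test understates a real benefit. In both cases the randomisation, which the Background presents as the study's advantage over earlier uncontrolled work, is not used for the two main questions.

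**Working it through.** **Inputs from the documents.** 90 families, 45 per group (timeline); about 20% loss, leaving about 70 (Subject Recruitment & Screening). Check: 90 × 0.8 = 72, which agrees. I use 35 per arm. The documents give no sample size for the 2018 design.

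**Assumptions.** Two-sided alpha 0.05, a medium effect taken as d = 0.5, a range of pre-post correlations r, and a range of natural change. None of these is stated in the documents.

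**The plan's own figure.** The protocol says "sample size of 70 is sufficient to detect a medium size effect with a power of .80", without naming a test, alpha, effect metric or correlation, so it cannot be reproduced uniquely. Readings tried:
- Paired t-test at 0.5 SD of change: 34 pairs needed; power 0.82 in one arm of 35 and 0.98 on all 70. One test within each arm (2 × 34 = 68) fits.
- Regression with f² = 0.15 and two predictors: 68 needed; power 0.82 at 70. This also fits.
- Unadjusted two-sample t-test, 35 per arm: power 0.54; 64 per arm needed. This does not fit.

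**False positives with no treatment effect.** Let dz be the natural change divided by the SD of the change score. Power of the paired test comes from the noncentral t with n − 1 df and noncentrality dz·√n.

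| dz | n = 35 | n = 70 (both groups pooled) |
|---|---|---|
| 0.2 | 0.210 | 0.378 |
| 0.3 | 0.407 | 0.697 |

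In units of the score, the change is dz·√(2(1 − r)). For dz = 0.2 that is 0.20 SD at r = 0.5 and 0.13 SD at r = 0.8; for dz = 0.3 it is 0.30 and 0.19 SD. A small drift is enough.

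A simulation (20,000 trials, r = 0.7, 35 per arm, equal change in both arms, dz = 0 / 0.2 / 0.3) gave rejection rates of 0.048 / 0.214 / 0.411 for the paired test and 0.050 / 0.050 / 0.050 for between-arm ANCOVA.

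**Missed benefit when untreated stress rises.** With a true benefit of 0.5 SD and r = 0.7, dz = 0.5/√(2 × 0.3) = 0.645. At n = 35:
- no natural change: paired power 0.96
- rise of 0.2 SD of change: dz = 0.445, power 0.73
- rise of 0.3 SD of change: dz = 0.345, power 0.51

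ANCOVA on the same assumptions has power 0.82 whatever the common drift. The cost of the paired test is therefore about 10 to 31 points (0.82 − 0.73 from unrounded values, to 0.82 − 0.51).

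**Power of the replacement.** ANCOVA effect = d/√(1 − r²), noncentrality = effect × √(35/2), 67 df, d = 0.5.

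| r | Power, 35 per arm | Per arm for 0.80 |
|---|---|---|
| 0.5 | 0.66 | 49 |
| 0.6 | 0.73 | 42 |
| 0.7 | 0.82 | 34 |
| 0.8 | 0.93 | 24 |

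Power is 0.803 at r = 0.68.

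**Regression to the mean** is not counted. It matters only if the score used for entry is also the pre score. The 2018 materials point to a fresh PSI at baseline, and with a fresh baseline and independent errors, selection alone left the rejection rate at 0.050 in simulation.

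**The case against.** The tests are offered as examples, under a sentence saying what will primarily be used, so a between-arm test is not excluded. The moderation model would ordinarily carry an arm term. That is fair as far as it goes: the accurate statement is that no between-arm test is specified. But the only example given for each efficacy question cannot answer that question, and leaving the choice open allows it to be made after the data are seen.

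A paired test does match the Aim 2 hypothesis as worded. It does not match the causal wording of the analysis section, and it does not match Aim 4.

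The false-positive figures assume a natural fall, whereas the only direction the documents suggest is no change or a rise. With a rise of 0.2 SD of change and no effect, a false reduction appears in about 0.1% of trials. This stands as a limit on the 21% to 41% figures; it does not rescue the test, because a rise produces the opposite error.

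The analysis section belongs to the 2011-12 protocol, and nothing shows that it was meant to govern the 2018 comparison. This also stands. The conclusion is firmest for the waitlist design, and the sponsor should say which design the section covers.

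**Conclusion.** The concern holds and needs correcting before analysis. For both efficacy outcomes the named test does not use the randomised comparison and cannot support a causal statement; Aim 4 has no specified test of its hypothesis. That conclusion rests on the text alone. The sizes rest on assumed natural change: 21% to 41% false positives at n = 35 for a fall of 0.2 to 0.3 SD of change, or paired power of 73% to 51% against 82% for ANCOVA for an equal rise (d = 0.5, r = 0.7). The arithmetic is the same for a stress or a child-behaviour score.

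**What to change.** For analyses (1) and (2), replace the paired t-tests with a baseline-adjusted comparison of arms in all randomised families: ANCOVA of the post score on arm and the baseline-visit score (not the phone-screen score), or a mixed model with an arm-by-time contrast. Report within-arm change as descriptive. Reword the Aim 2 hypothesis as lower stress than in the comparison arm, name a between-arm test for Aim 3, and state which design the section governs.

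- *Waitlist design.* Compare Spring post-intervention (May 2012) with the Summer group's second pre-intervention assessment (June 2012). Of the 6-month follow-ups the protocol says "They will occur in November 2012 for the Spring group and in February 2013 for the Summer group". The Summer group is treated in June and July, before either date, so follow-up has no untreated control and is descriptive only.
- *Support-group design.* The comparator is concurrent, so the contrast can be made at post-intervention, 6 and 12 months.

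**Cost.** No new visit is needed for the waitlist contrast. The measures table has no separate column for the Summer group's second pre-intervention visit, so the plan should confirm that the outcome measures are collected there. The follow-up parts of Aims 2 and 4 lose their confirmatory status in the waitlist design.

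The power statement must be restated with its test, alpha, effect metric and correlation. The 0.82 for a paired test in one arm of 35 is at 0.5 SD of change, which equals 0.5 SD of the score only at r = 0.5; at that correlation ANCOVA gives 0.66. The stated 80% may therefore not survive. At r = 0.5 or 0.6, 49 or 42 completers per arm are needed. These figures are for completers and make no allowance for missing scores, two parents per family or group delivery, which the revised plan should also address.
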